
Exclusion Criteria:
	
 • Suspected or known to be sensitive or allergic to midge bites; • Participated in an interventional study (other than a biting insect challenge study) in the previous 3 months; • Participated in a biting insect challenge study in the previous 72 hours; • Aware of having any cardiovascular or respiratory disorder (whether active or inactive) (e.g. asthma); • Individuals with localized skin disorders affecting the forearm; • Allergic to any of the test product ingredients; • Extensive tattooing or other conditions of the forearm which would make interpretation of the bite test results difficult; • Women who are pregnant, nursing or intending to become pregnant; • Previous anaphylaxis; • Aware of having a compromised immune system;(an immune system that is temporarily or permanently incapable of working at full capacity); • Phobia of flying insects; • Travelled to a mosquito-borne disease endemic area in the last 3 months.

Efficacy Endpoint(s):
	
Primary: Median Complete Protection Time for the repellent products, tested against Culicoides nubeculosus midges.
 
Secondary: Percentage protective efficacy of the repellent products, tested against Culicoides nubeculosus midges.

Safety Endpoint(s):
	
Adverse event data will be collected and summarised.

Statistical Methods:
	
Median Complete Protection Time will be calculated using the Kaplan Meier survival-function.
 
Two-way analysis of variance followed by Tukey's tests or general linear mode will be used to compare the mean complete-protection time for the tested repellents

Investigation Site(s):
	
Single-centre: Arthropod Control Product Test Centre (arctec), Chariot Innovations Limited, a wholly-owned subsidiary of the London School of Hygiene & Tropical Medicine (LSHTM).

TABLE OF CONTENTS

1. INTRODUCTION.....	7
2. OBJECTIVES.....	7
3. STUDY DESIGN	7
3.1. STUDY ENDPOINTS.....	8
3.2. RISKS AND BENEFITS	8
3.2.1. Midges	8
3.2.2. Product	8
4. PARTICIPANT ENTRY	9
4.1. SCREENING PROCEDURES	9
4.2. INCLUSION CRITERIA	9
4.3. EXCLUSION CRITERIA	10
4.4. WITHDRAWAL CRITERIA.....	10
5. RANDOMISATION AND ENROLMENT	11
6. TREATMENTS	11
7. SAFETY REPORTING FOR NON-DRUG TRIALS.....	12
7.1. DEFINITIONS	12
7.2. REPORTING PROCEDURES	12
7.2.1. Non serious AEs	12
7.2.2. Serious AEs	12
8. TEST METHODOLOGY.....	13

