APPENDIX 3: FLOWCHART FOR SAFETY REPORTING24

APPENDIX 4: SAMPLE SIZE CALCULATION FOR A COMPARISON TRIAL BETWEEN A POSITIVE CONTROL AND TWO MIDGE REPELLENT PRODUCTS.....25

1. Introduction

Mosquitoes, midges and other biting insects are vectors of extremely important diseases such as malaria, yellow fever, filariasis and many viruses and also may be of great nuisance value. The use of repellent products can provide added personal protection from disease transmission and nuisance bites. New effective repellents would offer an additional option for protection against biting insects. The tests carried out by *arctec* provide important information on the effectiveness of skin repellents, which will be used for label claims to accurately inform consumers and registration purposes.

The aim of this study is to determine the effectiveness of two topically applied insect repellent products provided by NEO-INNOVA HEALTHCARE LIMITED and one positive control containing the UK repellent brand 'Smidge'.

2. Objectives

Primary objective: To determine and compare the median complete protection time (CPT) of two insect repellent products and a positive control against *Culicoides nubeculosus* (midges).

Secondary objective: To determine and compare the protective efficacy of two insect repellent products and a positive control against *Culicoides nubeculosus* (midges).

3. Study Design

This is a single-centre, single-arm study with all participants testing two formulations containing PMD and a positive control product containing Picaridin. The control for each test is an untreated arm. There is no blinding or randomisation employed, since the outcome measures are based on midge behaviour. Repellent product testing takes place in a laboratory setting using 7 participants (preferably gender balanced). Each participant will test both PMD formulations and a positive control product (see section 8).

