9.2. Data analysis

The endpoint for Complete Protection Time will be time to treatment failure for each participant test. Treatment failure is the time at which the product no longer provides complete protection, which is determined as the time at which one probe or bite occurs in a 1 minute test, followed by a confirmatory probe or bite within 30 minutes. Using IBM SPSS Statistics 20, the times to treatment failure will be analysed using Kaplan-Meier Survival functions, and from these the median Complete Protection time and 95% confidence intervals will be calculated.

A linear regression will be used to compare the mean complete-protection time for the tested repellents. As a sensitivity analysis we will use linear regression to estimate the mean CPT difference between groups, but we will generate robust standard errors by relaxing the assumption of independence of observations between the same participant within the study, allowing for correlation between observations from the same participant in the variance-covariance matrix.

The Protective Efficacy over time from application will be calculated using the formula below at each hour and presented as a summary table and graph. Using IBM SPSS Statistics 20, the PE will be analysed using a two-way analysis of variance followed by Tukey's tests or generalised linear model.

$$PE = \frac{\text{Midges probing on control} - \text{Midges probing on treatment}}{\text{Midges probing on control}} \times 100$$

Adverse Events will be tabulated and included in the study report. Adverse events occurring after the end of participant participation but before the end of the study will be listed separately.

10. Safety and Data Monitoring

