Appendix 3: Flowchart for Safety Reporting

Appendix 4: Sample Size Calculation for a comparison trial between a positive control and two midge repellent products

A sample size calculation was done using CPT data from a previous study of a repellent against *Culicoides nubeculosus*. The sample size was calculated using the sample size formula for the comparison of 2 means with equal standard deviation. The required sample size per group is given by:

$$n = \frac{2\sigma^2}{\delta^2} f(\alpha, \beta)$$

Where δ^2 is the difference between the mean CPTs of 2 treatment groups, σ is the standard deviation of both treatment groups for one comparison which are assumed to be equal. $f(\alpha, \beta) = (z_{1-\alpha/2} + z_{1-\beta})^2$, which varied depending on the specified values of α and β .

Sample size calculation outcomes

The analysis revealed that for an experiment to compare mean CPT (in min) between any PMD products with Picaridin 20%, assuming a difference in mean CPT of 120 min, with a power of 80% and a significance level of 5%, 7 participants would be required.

A Bonferroni correction was applied for this analysis. The significance level at 5% ($\alpha = 0.05$) was divided by the number of comparisons being made to maintain overall significance level (here divided by 2, as 2 concentrations of PMD are being compared to Picaridin 20%).

Sample size calculation outcomes (with Bonferroni correction) when comparing between two PMD midge repellents and a Picaridin positive control.

Assumption of difference in mean CPT between any PMD group with Picaridin group (minutes)	Number of participants required per arm		
	Alpha = 5% Power = 70%	Alpha = 5% Power = 80%	Alpha = 5% Power = 90%
60	21	26	33
80	12	15	19
100	8	10	12
120	6	7	9
180	3	3	4

If only two arms are compared a Bonferroni correction would not be necessary and the numbers of participants needed for the study are slightly smaller.

Sample size calculation outcomes with the assumption of difference in mean CPT between one midge repellent and a Picaridin positive control.

Assumption of difference in mean CPT between PMD and Picaridin group (minutes)	Number of participants required per arm		
	Alpha = 5% Power = 70%	Alpha = 5% Power = 80%	Alpha = 5% Power = 90%
60	17	21	28
80	10	12	16
100	6	8	10
120	5	6	7
180	2	3	4

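### The 2.5% per-comparison rule behind the sample size is missing from the analysis, and section 9.2 and the synopsis give different models for comparing mean complete protection time

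*Combined protocol and SAP*

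**What the plan says.** - **Appendix 4** counts two comparisons of mean CPT, 40% PMD v Picaridin and 35% PMD v Picaridin. It applies a Bonferroni correction in which 5% is "divided by the number of comparisons being made to maintain overall significance level". It adds that no correction would be needed if only two arms were compared. The result is 7 participants for a 120 min difference at 80% power.
- **Section 9.2** says "A linear regression will be used to compare the mean complete-protection time for the tested repellents". It gives no significance level, list of contrasts or adjustment. A second regression, labelled a sensitivity analysis, uses robust standard errors, "relaxing the assumption of independence of observations between the same participant within the study".
- **Section 9.2** keeps ANOVA with Tukey for the secondary endpoint: "the PE will be analysed using a two-way analysis of variance followed by" Tukey's tests or a generalised linear model.
- **The synopsis (Statistical Methods)** gives CPT either two-way ANOVA with Tukey or a second option: "general linear mode will be used to compare the mean complete-protection time for the tested repellents".
- **Section 3** makes the data repeated measures: "Each participant will test both PMD formulations and a positive control product".

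**The concern.** The sponsor chose to protect an overall 5% level and sized the trial on that basis, but the analysis text drops the protection. Because only the sensitivity analysis in section 9.2 relaxes independence within participant, the main regression appears to treat the 21 results (7 participants x 3 products) as independent. The synopsis adds another model with another multiplicity rule, and nothing says which text governs.

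The mean-CPT model is the only between-product comparison of CPT that the plan specifies, and the primary objective is to determine and compare CPT. If the level and model are open, they can be chosen after the data are seen. If the silence of section 9.2 is read as 5% per comparison, the overall 5% that Appendix 4 set out to keep is not assured.

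**Working it through.** **Inputs.** From the documents: 7 participants, 3 products each, a 120 min difference, 80% power, two-sided testing, and 2.5% for each of two comparisons. Assumed, because the documents do not give them: the SD (back-solved below), normally distributed CPT, and within-participant correlation from 0 to 0.5.

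**1. Reproduce Appendix 4.** The formula is n = 2σ²(z₁₋α/₂ + z₁₋β)²/δ², rounded up. With σ = 68.9 min:
- at 2.5%: 2 x 68.9² x (2.2414 + 0.8416)² / 120² = 6.27, so 7, as stated;
- at 5%: 2 x 68.9² x (1.9600 + 0.8416)² / 120² = 5.18, so 6, as in the second table.

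This SD reproduces all 30 cells of the two tables. If 5% is used in the Bonferroni table instead, no SD fits more than 12 of its 15 cells. The 2.5% level was therefore really used.

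**2. Critical values under each reading.**

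| Reading | df | 5% each | 2.5% each |
|---|---|---|---|
| Regression ignoring participant | 18 | 2.101 | 2.445 |
| Product and participant factors | 12 | 2.179 | 2.560 |
| Two-way ANOVA, Tukey over three pairs | 12 | 2.668 | (own rule) |

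The synopsis does not name the two ANOVA factors; product and participant are assumed.

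**3. Overall error for the two comparisons with no true difference** (400,000 simulated trials per correlation).

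| Correlation | Ignoring participant, 5% each | Ignoring participant, 2.5% each | Participant term, 5% each | Participant term, 2.5% each |
|---|---|---|---|---|
| 0 | 8.9% | 4.5% | about 9% | about 4.5% |
| 0.1 | 7.3% | 3.5% | about 9% | about 4.5% |
| 0.2 | 5.6% | 2.6% | about 9% | about 4.5% |
| 0.3 | 4.2% | 1.9% | about 9% | about 4.5% |
| 0.5 | 2.0% | 0.8% | about 9% | about 4.5% |

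The regression that ignores participant becomes conservative as correlation rises. It uses the full σ², while the true variance of a difference is 2σ²(1 - correlation)/7. Tukey gives 3.7% for the two comparisons.

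**4. Sensitivity analysis.** With participant-clustered errors (factor (7/6)(20/18), no participant terms), overall error depends on the reference df, which section 9.2 does not state. At 2.5% each it is 3.9% on 6 df and 7.9% on 18 df. At 5% each it is 7.8% and 12.6%.

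**5. How often the verdicts differ for at least one PMD product**, both products truly different from Picaridin, over correlations 0 to 0.5.

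| Comparison of readings | 80 min | 120 min |
|---|---|---|
| 5% v 2.5%, same model | 20-28% | 4-18% |
| Section 9.2 (ignoring participant, 5% each) v synopsis (ANOVA with Tukey) | 25-34% | 10-27% |

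The direction is not fixed. At 80 min and zero correlation, some product is significant only under section 9.2 in 33% of trials and only under Tukey in 1%. At correlation 0.5 these become 8% and 23%.

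**6. Power at n = 7 for 120 min.** On the document's formula the standard error is 68.9 x √(2/7) = 36.83 and 120/36.83 = 3.258. Power is Φ(3.258 - 2.241) = 84.5% at 2.5% and Φ(3.258 - 1.960) = 90.3% at 5%. On noncentral t with 12 df and SD 68.9 x √(1 - correlation), a product-plus-participant model at 2.5% gives 75% at zero correlation, 80% at about 0.11, 84% at 0.2 and 97% at 0.5. A regression ignoring participant gives 78% on 18 df at zero correlation.

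**The case against.** **The texts can be reconciled.** The synopsis offers a general linear model as its second option, and the section 9.2 regression is one. Section 9.1 refers to Appendix 4, so 2.5% could be taken as implied. The Tukey wording may have strayed from the Protective Efficacy sentence. All of this is plausible. But an unclosed either/or leaves the choice open, and neither the regression nor the general-linear-model option states an adjustment.

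**The primary endpoint is a Kaplan-Meier median, and no success criterion is set on mean CPT.** This is true and limits the weight of the point: the medians and their intervals do not change. The sample size nevertheless rests on the comparison of means.

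**Inflation is not shown.** This stands in part. Section 9.2 lists no model terms; that it ignores participant is an inference from the sensitivity analysis. On that reading, 5% per comparison no longer exceeds 5% overall from a correlation of about 0.3. The 9% arises with a participant term, or with no correlation.

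**The disagreement figures pair a loose reading of one text with a strict reading of the other.** They do, and they combine model and level effects. The same-model comparison, at 4-18% for 120 min, isolates the level. CPT is read at hourly or half-hourly tests and stops at 12 hours, so all these rates are approximate.

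**The objective compares all three products, so Tukey's three pairs could be the intended family.** That would be coherent, but Appendix 4 counts only two comparisons. Tukey on 12 df would give 71% power for 120 min at zero correlation (SD 69 min).

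**Conclusion.** The concern holds and should be fixed before the data are analysed. The textual conflict needs no assumption: Appendix 4 tests two comparisons at 2.5% each, section 9.2 states no level and allows for participant only in its sensitivity analysis, and the synopsis permits a different model with a different multiplicity rule.

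The size rests on the assumed SD, normality and correlation. Verdicts from the two texts would differ for at least one product in roughly one trial in ten to one in four at the planned 120 min, and in a quarter to a third at 80 min. Neither text is always the stricter. Overall error at 5% each ranges from about 9% down to 2.0%, depending on how participant is handled; at 2.5% each it stays below 5% in both regression models. The sample size of 7 reproduces and is not in question.

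**What to change.** - State one identical CPT model in section 9.2 and the synopsis: a linear model with product and participant as factors, because every participant tests all three products.
- Name two contrasts, 40% PMD v Picaridin and 35% PMD v Picaridin, each tested at two-sided 2.5% with a 97.5% confidence interval.
- Delete ANOVA with Tukey as an option for CPT in the synopsis, and replace its loosely worded linear-model option with the named model. The Protective Efficacy analysis is not part of this change.
- Report 40% v 35% PMD descriptively, outside the 5%, since Appendix 4 does not count it.
- For the robust-error sensitivity analysis, specify a t reference on 6 df (participants minus 1) and say whether participant terms are kept. At 2.5% each, overall error on 6 df is 3.9% without them and a conservative 1.7% with them.

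The cost is wording in two places and a stricter threshold than an unadjusted 5%. N stays at 7. The sponsor should know that the named model falls short of 80% power for 120 min if within-participant correlation is below about 0.11 (75% at zero) and exceeds it above that.
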